### 6.3 Pharmacokinetics/pharmacodynamics (PK/ PD)

Plasma concentration of Eliapixant for all subjects will be listed in the clinical study report by dose and by planned sampling time window.

Under a separate cover a Population PK / PD analysis will be performed.

## 6.4 Safety

### 6.4.1 Adverse Events (AEs)

All AEs will be collected from signing the informed consent until the SFU visit.

All safety analyses will be performed on the Safety Analysis set (SAF).

The incidence of TEAEs will be assessed as secondary safety endpoint. The incidence of AEs and TEAEs will be analyzed by descriptive statistics, such as frequency tables.

An overall summary of the number and percentage of patients with AEs and TEAE will be presented. In addition, all AEs and TEAEs will be tabulated according to the affected system organ class and preferred term, as coded by the Medical Dictionary for Regulatory Affairs (MedDRA).

The frequency of the AEs related to potential and identified risks of Eliapixant will be displayed. Regarding the identification specifications for these AEs, the following SMQs and PTs will be applied:

- SMQ “Taste and smell disorders”
- SMQ “Haemorrhages”
- MLG Hypotension
  - PT: Blood pressure ambulatory decreased;
  - PT: Blood pressure decreased;
  - PT: Blood pressure diastolic decreased
  - PT: Blood pressure systolic decreased;
  - PT: Diastolic hypotension
  - PT: Hypotension;
  - PT: Mean arterial pressure decreased
- + other PTs of interest
  - PT: Heart rate decreased
  - PT: Bradyarrhythmia
  - PT: Bradycardia
  - PT: Sinus bradycardia
  - PT: Dizziness
  - PT: Dizziness postural
  - PT: Dizziness exertional
  - PT: Syncope
  - PT: Presyncope
  - PT: Loss of consciousness
  - PT: Blood pressure orthostatic decreased;
  - PT: Orthostatic hypotension;
- SMQ “Drug related hepatic disorders - comprehensive search”

Further tables will be provided for serious and/or drug related TEAEs. Tables for non-serious TEAEs will also be provided.

In addition, a separate table summarizing TEAEs that occurred in more than 5% of the subjects in any treatment group will be provided.

The incidence of all AEs during pre-treatment and during post-treatment (that is, AEs occurring more than 14 days after end of treatment with study drug) will be tabulated separately.

The summaries will be tabulated by intervention group and overall.

Serious adverse events, deaths and adverse events leading to discontinuation will be listed. The date, relative day (to study intervention) and treatment-emergent flag will be included.

Further summaries of adverse events by intensity and worst outcome, may be provided, consistent with Bayer Global Medical Standards.

#### 6.4.1.1 Taste-related and smell-related AEs

Impairment or loss of smell and/or taste is a common symptom of COVID-19. Taste-related/smell-related AEs as well as the responses to the questions of the taste/smell disturbance assessments will be analyzed using descriptive statistics.

To distinguish P2X3 related taste AEs from COVID-19 related smell/taste AEs the details of smell/taste disturbance assessments will be evaluated together with the SARS-CoV-2 test results, the AEs confirming COVID-19 and the timing information by medical review.

The following list of MedDRA PTs defines the SMQ “Taste and smell disorders”.

In addition, the following preferred terms will be combined into the PBMQ “Taste AE”:

- PT: Ageusia
- PT: Dysgeusia
- PT: Gustometry abnormal
- PT: Hallucination, gustatory
- PT: Hypergeusia
- PT: Hypogeusia
- PT: Taste disorder

The following preferred terms will be included in the “Smell-related AEs” category:

- PT: Anosmia
- PT: Congenital anosmia
- PT: Hallucination, olfactory
- PT: Hyposmia
- PT: Olfactory nerve disorder
- PT: Olfactory test abnormal
- PT: Parosmia

Taste- and smell-related AEs, along with responses about frequency and bothersomeness, will be analyzed using descriptive statistics.

In addition, the dose-dependency of taste-related AEs will be assessed using a logistic regression model with treatment as factor. The odds ratio and its 80% and 95% confidence intervals, and the p-value for treatment comparisons from the logistic regression model will be provided. Only taste-related AEs that cannot be attributed to a SARS-CoV-2 infection will be considered for the model.

#### 6.4.2 Study Treatment Duration and Exposure

Study treatment duration and the average daily dose will be summarized overall for SAF.

The average daily dose will be summarized descriptively by treatment group and overall. In addition, it will be categorized into the following groups:

- < 20mg
- >= 20mg to <= 30mg (80%-120% of 25mg)
- > 30mg to < 60mg
- >= 60mg to <= 90mg (80%-120% of 75mg)
- > 90mg to < 120mg
- >= 120mg to <= 180mg (80%-120% of 150mg)
- > 180mg

and summarized by treatment group and overall.

The duration of study treatment (in days) is derived by the following formula:

last dose date – first dose date + 1- number of days treatment was interrupted due to COVID-19 pandemic-related reasons.

Descriptive statistics of treatment duration will be presented.

The number of tablets taken will be summarized descriptively by treatment group and overall.

Using the drug accountability data, the average daily dose for overall study is calculated for subjects on active treatment based on the following formulas depending on the treatment arm:

For the 25mg treatment arm

$$25\text{mg} \cdot \frac{\frac{1}{3} \cdot \text{Total Number of 25mg tablets taken}}{\min(\text{last tablets returned date, last treatment intake date}) - \text{first tablets dispensed date}}$$

For the 75mg treatment arm

$$25\text{mg} \cdot \frac{\text{Total Number of 25mg tablets taken}}{\min(\text{last tablets returned date, last treatment intake date}) - \text{first tablets dispensed date}}$$

For the 150mg treatment arm

$$25\text{mg} \cdot \frac{\frac{2}{3} \cdot \text{Total Number of 25mg tablets taken}}{\min(\text{last tablets returned date, last treatment intake date}) - \text{first tablets dispensed date}} + 100\text{mg} \cdot \frac{\text{Total Number of 100mg tablets taken}}{\min(\text{last tablets returned date, last treatment intake date}) - \text{first tablets dispensed date}}$$

Overall Compliance will be calculated as

$$\frac{\text{Total Number of 25mg tablets taken} + 4 \cdot \text{Total Number of 100mg tablets taken}}{14 \cdot (\min(\text{last tablets returned date, last treatment intake date}) - \text{first tablets dispensed date})}$$

Compliance between visits will be calculated as

$$\frac{\text{Number of 25mg tablets taken between visits} + 4 \cdot \text{Number of 100mg tablets taken between visits}}{14 \cdot (\min(\text{tablets returned date; last treatment intake}) \text{ at Visit } x - \text{tablets dispensed date at Visit } (x - 1))}$$

If compliance between two consecutive visits cannot be determined (e.g., if a patient does not return medication at the scheduled time), then compliance will be averaged across the periods that are affected.

For between-visit compliance, periods from unscheduled visits are assigned to nearest scheduled between visit periods.

The compliance will be summarized descriptively by treatment group and overall. In addition, compliance will be categorized into three groups (<80%, 80-120%, >120%) and summarized by treatment group and overall.

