6.1 Study Interventions Administered

- Each participant will be randomized to receive one of three oral doses of BAY 1817080 or placebo, administered twice daily
- Participants should be instructed to take the morning dose of study intervention at approximately the same time of day, every day over the course of 12 weeks. The interval between the application of the morning and the evening dose should be with an interval of approximately 12 hours.
- The morning dose should be taken at the site on the second day of Visit 6 (see also Section 8.5)
- Tablets are not to be broken, halved or crushed; they should be swallowed as a complete unit with water.
- Tablets can be taken with or without food. See Section 8.5 for detailed instructions regarding recording of the drug intake and the food intake before or after the drug intake in relation to blood sampling for PK.
- Participants will have to confirm the tablet intake twice per day by reporting this on the handheld device. In addition, the time of the tablet intake will be collected.
- If a dose of study intervention has been missed:
 - If ≤ 6 hours has passed since the dose was due, it should be taken immediately
 - If > 6 hours have passed since the dose was due, the dose should be skipped and the next dose should be taken according to the regular schedule.

Table 6–1: Study Interventions Administered

	BAY 1817080	Placebo
Intervention Name	BAY 1817080	Placebo for BAY 1817080
Type	Drug	Placebo
Dose formulation	Tablet	Tablet
Unit dose strengths	25 mg and 100 mg	NA (Placebo for BAY 1817080 25 mg and BAY 1817080 100 mg)
Dosage Levels	25 mg or 75 mg or 150 mg BID	NA (Placebo)
Route of Administration	Oral	Oral
Packaging and Labeling	Tablets will be provided in blisters. Study intervention will be labeled as required per country requirement.	

Abbreviations: BID = twice daily; NA = not applicable

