## 3. Study Design

This is a randomized, placebo-controlled, double-blind, parallel group, multi-center phase 2b dose-finding, efficacy and safety study.

The study population consists of participants with a cough that has lasted for at least 12 months (unresponsive to treatment options) with a diagnosis of refractory chronic cough and/or idiopathic (unexplained) chronic cough and with persistent cough for at least the last 8 weeks before screening.

Approximately 337 participants will be screened to achieve 236 randomly assigned to study intervention and 200 evaluable participants for an estimated total of 50 evaluable participants per intervention group. The number of participants to be randomized might be increased if more participants than expected become unevaluable due to COVID-19 related circumstances, to maintain the goal of 50 evaluable participants per intervention group.

Following screening, eligible participants will be randomized to one of four parallel intervention groups in a 1:1:1:1 ratio.

After randomization, each participant will receive one of three doses of Eliapixant (25 mg, 75 mg or 150 mg) or placebo administered orally with or without food, twice daily (BID) over the course of 12 weeks.

After last intake of study intervention, participants will enter an observational safety follow-up period of 30±5 days. During this period, AEs will continue to be collected.

The study will be analyzed once all participants have completed treatment. The last end of treatment/premature discontinuation visit will be the cut-off date for the primary completion analysis. With that, the full efficacy data will be available, and a full analysis will be provided for

all available data. The study will continue with the safety follow-up for the remaining participants and the final analysis for the study will occur at the conclusion of the study. All measures to restrict access to unblinding data until the final database closure are described in the study blinding plan, that is approved and signed prior to the first unblinding of the database.

For details regarding the Pre-intervention, Intervention and Post-Intervention Period see CSP section 4.1.

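### SAP 6.4.2 computes dose per day over both BID intakes but bins it against single-intake doses, so the exposure bands sit at half the planned daily totals

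*SAP*

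**What the plan says.** SAP section 3 describes "one of three doses of Eliapixant (25 mg, 75 mg or 150 mg) or placebo administered orally with or without food, twice daily (BID"), and Table 6-1 in Protocol section 6.1 gives the dosage levels as "25 mg or 75 mg or 150 mg BID". The stated doses are therefore amounts per intake, with two intakes a day.

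SAP section 6.4.2 states: "Using the drug accountability data, the average daily dose for overall study is calculated for subjects on active treatment". There is one formula per active arm. Each adds up the active milligrams in the tablets taken and divides by a number of days. None contains a factor of one half, and placebo has no dose formula.

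The result is then grouped, by treatment group and overall. Three of the seven bands carry a reference dose: ">= 20mg to <= 30mg (80%-120% of 25mg"), ">= 60mg to <= 90mg (80%-120% of 75mg") and ">= 120mg to <= 180mg (80%-120% of 150mg"). The other four are the gaps between these bands and the two open ends.

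The same section has compliance formulas with a divisor of 14 tablet units a day, one 100 mg tablet counting as four units. It adds that "compliance will be categorized into three groups (<80%, 80-120%, >120%) and summarized by treatment group and overall".

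**The concern.** The variable is a daily total, but the reference doses in the band labels are single-intake doses. The label percentages are correct for 25, 75 and 150 mg. Those references, however, are half of what a fully adherent participant takes in a day.

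The bands invite reading as the intended range for each arm, because they use the same 80% and 120% limits as the compliance classes. Read that way, the table misleads. Correct dosing in the two higher arms looks like excess dosing, and half dosing looks like full adherence. In a dose-finding study, the table of dose received should not do this.

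**Working it through.** **Inputs.** Let *a* and *b* be the 25 mg and 100 mg tablets (active plus placebo) taken per day. From SAP 6.4.2:

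- dose, 25 mg arm: 25 × *a*/3
- dose, 75 mg arm: 25 × *a*
- dose, 150 mg arm: 25 × (2/3)*a* + 100*b* = 50*a*/3 + 100*b*
- compliance: (*a* + 4*b*)/14

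**The plan's band edges.** 0.8 and 1.2 times 25, 75 and 150 mg give 20-30, 60-90 and 120-180 mg. The printed limits are reproduced exactly, but only from the single-intake doses.

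**Full daily intake.** BID dosing alone gives 2 × 25 = 50, 2 × 75 = 150 and 2 × 150 = 300 mg a day. The SAP's formulas agree. Neither document prints the tablet schedule, so it is inferred. Full compliance needs *a* + 4*b* = 14, and the one-third and two-thirds shares need *a* divisible by 3. For *b* = 0, 1, 2, 3, *a* is 14, 10, 6, 2, and only *a* = 6, *b* = 2 fits. Table 6-1 supports this, since it lists placebo for both strengths: "NA (Placebo for BAY 1817080 25 mg and BAY 1817080 100 mg").

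**Results when both strengths are taken in this 6:2 ratio (mg/day):**

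| Arm (BID) | Full intake | At 40%-60% compliance | At 80%-120% compliance | Where 80%-120% falls |
|---|---|---|---|---|
| 25 mg | 25 × 6/3 = 50 | 20-30 | 40-60 | gap above 30 and below 60 mg (exactly 60 falls in the band for 75 mg) |
| 75 mg | 25 × 6 = 150 | 60-90 | 120-180 | band labelled for 150 mg |
| 150 mg | 50 × 6/3 + 100 × 2 = 300 | 120-180 | 240-360 | above 180 mg |

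The 40%-60% column is the band labelled for the participant's own dose in every arm, and the SAP classes that compliance as below 80%.

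**150 mg arm without any tablet-pattern assumption.** Since 100*b* ≥ (50/3) × 4*b*, the dose is at least (50/3)(*a* + 4*b*) = (50/3) × 14 × compliance = 233.3 × compliance. Overall compliance of 80% or more therefore gives at least 186.7 mg, always above 180 mg. This uses overall compliance, which shares the dose formula's denominator. At the planned ratio the top class starts just above 60% compliance (180/300). It therefore pools part of the below-80% class with the other two.

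**Alternative readings.**

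- Day count: the denominator is a date difference with no added day. With 169 intakes over 84 days the results are 50.3, 150.9 and 301.8 mg, in the same bands.
- Once-daily intake (*a* = 3, *b* = 1) would give 25, 75 and 150 mg and fit the bands. The SAP's compliance formula would then return 7/14 = 50%.

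**The case against.** The strongest reply is that nothing here is miscalculated. The formulas are valid, each label is literally true of its stated reference, and no label says that its band is the target for an arm. In the 75 mg arm, 120-180 mg is in fact 80%-120% of the correct daily total of 150 mg. This stands as a description: the fault is a mismatch of scale within one section. It does not remove the mismatch, because a daily variable is still banded around per-intake doses.

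A second reply is that little is lost. The table is split by treatment group, so the arm is known. The continuous dose summary, tablet counts and compliance classes are reported separately, and the validity rules for cough counts and the per-protocol set use compliance. This is right and limits the rating to minor.

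A third is that the 40%-60% result assumes planned-ratio intake. That fits the missed-dose instruction in Protocol section 6.1, which concerns whole doses, but it is not guaranteed. With uneven omission and no extra tablets, the own-dose band in the 25 and 75 mg arms needs *a* = 2.4-3.6. Compliance then runs from 2.4/14 = 17% to (3.6 + 8)/14 = 83%. In the 150 mg arm the range is 4.8/14 = 34% to 9.2/14 = 66%. A 25 or 75 mg participant could thus be at 80%-83% and still in the own-dose band, but only by omitting many 25 mg tablets and almost no 100 mg tablets. The factor of two does not depend on the ratio.

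**Conclusion.** The inconsistency is real and follows from the SAP's own formulas and the BID schedule: the band references are half the planned daily totals in all three active arms. Under planned-ratio intake, a participant with 80%-120% compliance never falls in the band labelled for the assigned dose. In the 75 mg arm the 120-180 mg band still separates the compliance classes correctly, but under a label for another dose. In the 150 mg arm the table cannot distinguish 80%-120% from higher compliance.

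Severity is minor. The error is confined to one descriptive table on the safety analysis set; placebo and all inferential analyses are unaffected. Only the exact compliance percentages rest on the inferred tablet schedule and planned-ratio intake. The 50, 150 and 300 mg totals and the 186.7 mg bound do not.

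**What to change.** Put formulas and bands on one scale. Either option changes reporting only, not dosing.

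- **Option 1, daily scale.** Keep the formulas and use: below 40; 40-60 (80%-120% of 50 mg/day); above 60 to below 120; 120-180 (80%-120% of 150 mg/day); above 180 to below 240; 240-360 (80%-120% of 300 mg/day); above 360 mg.
- **Option 2, per-intake scale.** Divide each formula by 2, keep the printed bands, and rename the variable as average dose per intake.

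Under either option, a table footnote should say that the bands describe active dose received and match the compliance classes exactly only when both strengths are taken in the planned ratio. For example, in the 25 mg arm, 4.7 tablets of 25 mg and 2 of 100 mg a day is (4.7 + 8)/14 = 91% compliance but 25 × 4.7/3 = 39.2 mg/day, just under the 40 mg limit.

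The cost is a few lines of SAP text and new cut-points, or a factor of one half, for one table. Data collection and all other analyses stay as they are.

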1.2 Schema

Figure 1–1: Study design

Abbreviations: BID = bis in die (twice daily); n= number of completers

Procedure	Screening	Intervention						Safety Follow-up	
		Visit	V2 ¹		V3	V4	V5		V6 ² /TV ³
Day (Relative to start of intervention)	-16 up to -14 days	-1	0	14±2	28±2	56±2	83±2	84±2	30±5
Week (Relative to start of intervention)	-2			2	4	8	12		
Adverse events ¹⁹	X		X	X	X	X		X	X
Prior and concomitant medication	X		X	X	X	X		X	X
Survival status ²⁰									X
Efficacy / patient report outcomes assessments									
Dispensation of cough recording device	X	X		X	X	X	X		
24-hour cough recording ²¹	X	X		X	X	X	X		
Dispensation of handheld device for diary completion	X								
SCCD data collection ²²	←=====→								
Cough Severity VAS ²³	←=====→								
LCQ ²⁴	X		X	X	X	X		X	X
EQ-5D-5L ²⁴	X		X	X	X	X		X	X
PGI-S ²⁴	X		X	X	X	X		X	X
PGI-C ²⁴				X	X	X		X	X

Abbreviations: ECG = electrocardiogram; EoI = end of intervention; EQ-5D-5L = European Quality of Life 5 Dimensions 5 Level Scale; IWRS = Interactive Web Response System; LCQ = Leicester Cough Questionnaire; PK = pharmacokinetics; PGI-C = patient global impression of change; PGI-S = patient global impression of severity; SCCD = Severity of Chronic Cough Diary; SFU = safety follow-up; TV = termination visit; V = visit

1. Visit 2 will be a 2-day visit. On the first day the cough recording device will be dispensed and cough recording started by the participant. On the second day, only after cough recording has been completed other procedures for Visit 2 can be performed.
2. Visit 6 will be a consecutive 2-day visit. On the first day the cough recording device will be dispensed and cough recording started by the participant. On the second day, only after cough recording has been completed other procedures for Visit 6 can be performed.
3. In case of premature discontinuation of the study intervention before week 12, a termination visit (TV) should be conducted. All procedures planned for Visit 6, with the exception of the sparse PK sampling and biomarker sampling, should be performed at the TV, preferably on the day of the last tablet intake.
4. The safety follow-up visit will be performed 30 (± 5) days after intake of the last tablet.
5. To assure timely drug supply to each study site, the recording of randomization must be completed at least 1 day but not later than 4 days after Visit 1 (before Visit 2).

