7.1 Discontinuation of Study Intervention

It may be necessary for a participant to permanently discontinue study intervention. Such events are expected to be rare.

If study intervention is discontinued, a participant who is still in the intervention period should have the EoI visit (Visit 6) assessments performed as soon as possible. Following Visit 6, the participant continues to the follow-up period and the end of study visit (i.e., the SFU visit) assessments thereafter according to the SoA.

Participants *must* discontinue study intervention if any of the following occurs:

- In the investigator's opinion, continuation of the study intervention would be harmful to the participant's well-being
- Liver safety-related discontinuation criteria are met as described in [Table 7–1](#).
- Pregnancy (see Sections [8.3.5](#) and [10.4](#)).

Table 7–1: Liver Safety-Related Monitoring and Discontinuation Criteria

Lab result	Measures
ALT or AST >3 x ULN	
 • Repeat testing of ALT, AST and TBL 2-3 times a week • Withdraw study intervention if the participant cannot come for a repeat testing* • 'Close observation' as defined in Section 8.3.6
ALT or AST >3 x ULN and TBL >2 x ULN	Withdraw study intervention and initiate close observation as outlined in Section 8.3.6
ALT or AST >3 x ULN and INR >1.5 x ULN**	Withdraw study intervention and initiate close observation as outlined in Section 8.3.6
ALT or AST > 3 ULN with appearance of fatigue, nausea, vomiting, right upper abdominal quadrant pain or tenderness, fever, rash and/or eosinophilia (>5%)	Withdraw study intervention and initiate close observation as outlined in Section 8.3.6
ALT or AST >5 x ULN for more than 2 weeks	Withdraw study intervention and initiate close observation as outlined in Section 8.3.6
ALT or AST >8 x ULN	Withdraw study intervention and initiate close observation as outlined in Section 8.3.6

* i.e., in case no visit for a repeat testing could be arranged within a reasonable time frame despite efforts to contact the participant

** Relevant only if the participant is not on Vitamin K antagonist or heparin

Abbreviations: ALT = alanine aminotransferase; AST = aspartate aminotransferase; INR = international normalized ratio, TBL = total bilirubin, ULN = upper limit of normal (all referring to serum)

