7.1.1 Rechallenge

Study intervention may be restarted after a temporary interruption if deemed clinically appropriate by the investigator in collaboration with the Bayer Medical Monitor.

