### **Per protocol set (PPS)**

All participants randomly assigned to study intervention, who have no validity findings affecting efficacy.

A list of potential validity findings will be provided in a separate important deviations and validity specifications document (Assessment Criteria and Identification Requirement (ACIR)) which will be finalized before database lock. The assignment of patients to this analysis set will be based on the assessment meetings.

The patients with invalid/missing baseline cough count measurements or only invalid/missing post-baseline cough count measurements will be excluded from the PPS.

Cough count measurements will be considered invalid if the duration of valid recording is less than 20 hours. If the treatment compliance between the previous visit and the visit of the cough count measurement is  $<80\%$  or  $>120\%$ , the measurement will also be considered invalid for the primary analysis.

Due to the repeated measurements design of the study a patient dropping out of the study may still be evaluable for efficacy and will therefore not be excluded from PPS. The minimum required treatment duration is up to including Visit 3 to allow for a valid post-baseline cough count measurement.

Participants will be analyzed according to the intervention they actually received. If participants received different interventions throughout the course of the study, they will be excluded from the PPS.

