#### Intercurrent events:

- a) Early discontinuation of study or study intervention for any reason: use data until discontinuation (while on treatment strategy). For handling the intercurrent event (ICE) of early discontinuation of the study and of the study intervention the while on treatment strategy will be applied. This strategy considers measurements of the endpoint up until the time of the intercurrent event. The last observation of the endpoint prior to the event will be used in the analysis. LOCF for all missing data due to early discontinuation will be applied.
- b) Non-compliance with study intervention: use data during compliant periods (while on treatment strategy) on a visit-by-visit approach:  
compliance will be calculated for the period between two consecutive visits. If the compliance is too low (i.e. below 80%), or too high (i.e. >120%, which is highly unlikely) the data collected during this period and the subsequent visit will not be used. Instead, the mean value of the observations between the adjacent compliant

visits (i.e. end point of the preceding compliant period and end point of the following compliant period) is taken. If there is no following period that can be used, LOCF will be applied. If there is no preceding compliant period, the mean value of the baseline value and the observation of the end of the first compliant period will be used.

- c) COVID-19 infection: use data prior to an active COVID-19 infection which is defined as the date of the first positive SARS-CoV-2 test or the date of the first positive serology IgG test or the start date of the AE confirming a COVID-19 infection (while on treatment), whichever is earliest. Symptoms of an acute COVID-19 infection are expected to have a major impact on the primary endpoint. Since long term effect of such an infection is unknown, only the data prior to the intercurrent event of an active COVID-19 infection will be used. LOCF imputation will be used in this case.

The **population** the primary estimand bases on is the population as described by the inclusion/exclusion criteria given in section 5 of the CSP and further by the PPS analysis population in section 5.1.

The **population-level summary** is the estimated geometric mean ratio (relative to baseline) of the primary efficacy variable by intervention group.

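### Read per visit, the between-visit compliance formula drops the off-drug days just before a cough recording, so an interruption still running at Visit 3, 4 or 5 can pass the 80–120% gate

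*SAP*

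**What the plan says.** Compliance decides which cough recordings enter the analysis. The PPS definition in SAP 5.1 looks at the interval leading up to each recording: "If the treatment compliance between the previous visit and the visit of the cough count measurement is" below 80% or above 120%, the recording is invalid for the primary analysis. Intercurrent event (b) in SAP 6.2.1 applies the same limits visit by visit ("compliance will be calculated for the period between two consecutive visits"). It replaces an excluded value by the mean of the adjacent compliant visits, or by LOCF if no usable period follows.

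The formula is in SAP 6.4.2. The numerator is "Number of 25mg tablets taken between visits" plus four times the corresponding count of 100 mg tablets. The denominator is 14 times a number of days. These run from the "tablets dispensed date at Visit" x−1 to the earlier of the tablets-returned date and the last treatment intake, both at Visit x. The average-dose and overall-compliance formulas beside it use the same pair of dates ("tablets returned date, last treatment intake") with no visit qualifier. The SAP does not define last treatment intake for the between-visit case.

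On stopping and restarting, Protocol 7.1.1 says: "Study intervention may be restarted after a temporary interruption". The intercurrent events in SAP 6.2.1 are early discontinuation, non-compliance and COVID-19 infection, so temporary interruption has no rule of its own. For discontinuation, event (a) uses data up to the event and carries the last prior observation forward. The Visit 6 procedures "should be performed at the TV, preferably on the day of the last tablet intake" (Schedule of Activities, footnote 3), and under Protocol 7.1 a participant who stops "should have the EoI visit (Visit 6) assessments performed as soon as possible". Neither sets a maximum gap.

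**The concern.** The primary estimand is while-on-treatment, and the compliance gate is how the SAP puts it into practice visit by visit. For a 24-hour recording, the days that matter most are those immediately before it. If the denominator ends at the last tablet, those are exactly the days it leaves out when dosing has paused. A participant can then be off drug at the recording, count as compliant, and supply an off-drug value as an on-treatment one. In an active arm that pulls the estimate towards placebo at the visit concerned. Because the key term is undefined, two programmers could also classify the same recording differently.

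**Working it through.** **1. The plan's constant of 14.** The factors 1/3 and 2/3 in the SAP 6.4.2 dose formulas imply three tablets of 25 mg size and one of 100 mg size per intake. With the weight of 4 this gives 2 × (3 × 1 + 1 × 4) = 14 units per day, as stated.

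**2. Per-visit reading, Visit 4 (day 28) to Visit 5 (day 56).** Full dosing, last intake on day s, interruption still running at Visit 5.
- Units taken: 14 × (s − 28 + 0.5) if the first dose from the new pack is the evening dose, or 14 × (s − 28 + 1) if both day-28 doses come from it.
- SAP denominator: 14 × (s − 28). Full-interval denominator: 14 × 28 = 392.

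| Last intake | Units taken | SAP denominator | SAP compliance | Over full interval | Days off at Visit 5 |
|---|---|---|---|---|---|
| Day 35 | 105–112 | 98 | 107–114% | 27–29% | 21 |
| Day 42 | 203–210 | 196 | 104–107% | 52–54% | 14 |
| Day 49 | 301–308 | 294 | 102–105% | 77–79% | 7 |

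All three pass 80–120% on the SAP formula, and all three are below 80% over the full interval. Counting whole days only, the SAP figure is 100% in each case, against 25%, 50% and 75%. In the 14-day intervals (Visits 2–3 and 3–4), being off for the last 3 or 7 days again gives 100% by whole days, against 11/14 = 78.6% and 7/14 = 50.0%.

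**3. Study-wide reading.** If last intake is the final one in the study, a participant who later resumes has a last intake after Visit x. The earlier date is then the tablets-returned date. Seven days on and 21 off scores 98/392 = 25% and is caught.

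**4. Visit 6.** Protocol 6.1 places the morning dose at the site on the second day of Visit 6, after the recording. Someone who was off for 21 of 28 days and takes that dose scores (14 × 7 + 7)/392 = 105/392 = 26.8%, and is caught on either reading.

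**5. Denominator run to the visit.** By whole days, gaps of 7, 14 and 21 days in a 28-day interval score 75.0%, 50.0% and 25.0%, all rejected. The longest final gap that still passes is 5 of 28 days (82.1%) or 2 of 14 days (85.7%).

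**6. Day count.** The last-intake branch subtracts two dates without adding a day, although treatment duration in the same section does add one. A last intake on day 30 gives 35/28 = 125% or 42/28 = 150%. An early stopper is thus labelled over-compliant, but the recording is still excluded. A last intake on the dispensing day gives a zero denominator.

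**7. Possible dilution.** Protocol 9.2 assumes a maximum effect of 0.35 on the log scale. The documents give no rate of such recordings. If 2%, 5% or 10% of an active arm contributed one with the effect fully lost (an assumption), the effect would fall by 0.02 × 0.35 = 0.007, 0.05 × 0.35 = 0.018 or 0.10 × 0.35 = 0.035.

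**The case against.** A reader might infer that anyone off drug for weeks has the recording counted as on-treatment and that the Week 12 primary endpoint is unprotected. The documents do not support that, for four reasons.

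- After a recorded permanent stop, event (a) discards later recordings whatever the compliance figure.
- In the neighbouring formulas last treatment intake date is plainly the participant's final one. On that reading resumed interruptions are caught (step 3).
- The Visit 6 site dose exposes a preceding gap (step 4).
- Someone who interrupts across Visit 5 and then resumes normally supplies a Week 12 value of their own.

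The PPS validity criteria are listed in a separate document that is not available here, so they may catch some cases. The protocol also expects discontinuation of study intervention to be rare.

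These points stand and narrow the concern, but they do not remove it. In the between-visit formula the words at Visit x follow the whole minimum, so the per-visit reading is the natural one, and the SAP does not rule it out. Event (a) does not say that discontinuation is dated at the last tablet. If it is dated at the termination visit, a late off-drug recording there becomes the last observation and is carried to Week 12. Compliance would score it at about 100% on either reading. The sensitivity analyses offer little protection, because the FAS analysis repeats the primary one and the COVID-19 variants keep events (a) and (b) unchanged.

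It is also tempting to say that footnote 3 and Protocol 7.1 contradict each other. They do not: a preferred day and as soon as possible are compatible. What is missing is an outer limit for analysis.

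**Conclusion.** The point holds in a limited form. On the per-visit reading, the formula admits recordings made during a temporary interruption still running at Visit 3, 4 or 5, with scores of 102–114% where full-interval compliance is 27–79%. The Week 2, 4 and 8 secondary endpoints are the ones mainly affected. Week 12 is reached only through the imputation rules, LOCF or the adjacent-visit mean. LOCF is the direct route, since no recording follows Visit 6. Gaps of weeks are possible only in the two 28-day intervals.

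Separately, the undefined discontinuation date leaves room for a late termination-visit recording to be used and carried forward. The missing day in the count is a labelling error that does not let off-drug recordings in.

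The number of participants affected is unknown. The 0.007–0.035 reduction rests on assumed rates and full loss of effect, and is small beside the planned SD of 0.8. This should be corrected before unblinding, but it does not show that the primary analysis fails.

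**What to change.** - **SAP 6.4.2:** end the between-visit denominator at the start of the cough recording at Visit x, or at the tablets-returned date if earlier, and not at last intake. Count doses due in place of a date difference, which also removes the day-count error.
- **SAP 6.2.1, event (a):** date discontinuation at the last dose. Before unblinding, prespecify the maximum gap between last dose and a usable termination-visit recording. The sponsor should choose and justify that limit. The documents give no basis for a particular figure, and one as tight as a single dosing interval would clash with the 80–120% tolerance and with the missed-dose instruction in Protocol 6.1.

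The cost is SAP wording and a small programming change. Intake times are already collected twice daily on the handheld device (Protocol 6.1). The downside is that a few more recordings may be classed as invalid. Short final gaps, up to 5 of 28 or 2 of 14 days by whole-day counting, would still pass the compliance gate.
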